6.0 Data Collection & Study Evaluations

6.1 Data Collection.

Data collected will include surveys, semi-structured qualitative interviews, and administrative data. The outcomes of interest for Aims 2 & 3 (acceptability, feasibility, functioning, and mechanisms), their source, and the specific measure (as applicable) are presented in Table 1. Couples will complete surveys prior to treatment (baseline), during treatment, and within four weeks of their final COACH session. Those who do not attend their final session will receive their survey by mail using CCDOR's modified-Dillman protocol.⁵⁴

Consistent with recommendations, we will obtain collateral reports on veteran functioning by asking LOs to report on the veterans' functioning on the Inventory of Psychological Functioning (IPF).⁵⁵ Veterans will also complete a posttreatment structured clinical interview for PTSD symptoms.⁵² Lastly, veterans and LOs will complete 90-minute semi-structured qualitative exit interviews.

All interviews will be conducted in person or by phone, based on the interviewee's preference, and will be audio-recorded. Qualitative exit interviews (Appendix 2) will assess (1) attitudes about intervention components, structure (e.g., level of therapist contact), and materials (e.g., handouts), (2) acceptability and efficacy of COACH, including suggestions for intervention improvement, (3) engagement with COACH, including retention and barriers/facilitators to

Table 1. Select Measures. See materials document for full list.

Domain	Reporter		Source			Measure
	V	LO	S	I	A	
Acceptability						
Treatment Structure	X	X	X	X		CES ⁵⁶ ; CSQ-8 ⁵⁷
Materials	X	X		X		N/A
Feasibility						
Treatment Retention	X	X		X	X	N/A
Treatment Fidelity				X		Fidelity instrument ^b
Screening Approach				X		N/A
Recruitment Approach				X		N/A
Assessment Process	X	X	X	X		All survey measures
Outcomes: Functioning						
Overall functioning	X	X	X			Short Form Survey ⁵⁸
MH functioning	X	X	X	X		CAPS-5 ⁵² , PCL-5 ⁵⁹ , PHQ-9 ⁶⁰
Self-care functioning	X	X	X			IPF ⁵⁵
Family functioning	X	X	X			IPF ⁵⁵
Romantic functioning	X	X	X			IPF ⁵⁵
Communication	X	X	X			Prepare/Enrich ⁶¹
Conflict Resolution	X	X	X			Prepare/Enrich ⁶¹
Parenting	X	X	X			IPF ⁵⁵
Social functioning	X	X	X			IPF ⁵⁵
Outcomes: Mechanisms						
Session Attendance				X		N/A
HW Compliance				X		PEAS ⁶²
Social control	X	X	X			Emotional and Problematic Support ⁶³
Subjective Norms	X	X	X			Subjective Norms-PTSD ^a
LO Reliance	X	X	X			Treatment Discussions ^a

^aUnpublished scale from Project HomeFront. ^bDeveloped during the study
V = Veteran; LO = Loved One; S = Survey; I = Interview; A = Administrative Data.

engaging with the program, (4) perceptions of the impact of the program on the intervention targets (e.g., functioning, social control, subjective norms, and LO reliance) and exploration of unexpected domains impacted by the program, and (5) the completeness and time burden of the survey battery. We will also extract the following administrative data: (1) the number of sessions attended (from electronic medical record; retention), (2) the number of participants screened each month (screening), and (3) the number of eligible veterans and LOs who declined participation (recruitment),

and therapists' ratings of homework compliance using two items adapted from the Patient Exposure and Response Prevention Adherence Scale (PEAS) for Obsessive Compulsive Disorder (also a cognitive-behavioral exposure therapy).⁶²

6.2 Fidelity Checklists and Provider Training.

Over the course of the open trial, [name] will lead efforts to finalize fidelity checklists, and [name] will lead efforts to develop the provider training program. We anticipate the provider training program will follow a structure similar to that of the VA's national PE and ICBT trainings. These include an initial didactic training with role plays (PE is 4 days; ICBT is 2.5 days) followed by two training cases with individual feedback and weekly case consultation. Additional materials needed for the training program (e.g., powerpoint, clinical vignettes, role play exercises) will be included in the final RCT manual for COACH. Each therapy session will be recorded. We will apply the fidelity checklists to one randomly selected session for each couple. We will identify gaps in content covered by checklist items and items that are unclear, difficult to rate, or not consistently applicable. Items will be revised and finalized for the final Stage II Manual.²⁵

6.3 Final RCT Manual.

During the conduct of the open trial, Drs. [name] and [name] will meet weekly and the larger team will meet monthly to discuss new observations, successes, and challenges. They will identify

portions of session recordings to review to illustrate examples. These discussions will be used to refine and expand the manual and to identify key questions for stakeholder meetings. We will meet with veteran and LO stakeholder groups once during the conduct of the open trial. Final stakeholder meetings, with all stakeholder groups, will take place during month 23 to review preliminary findings and obtain feedback on the Stage II manual.

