5.0 Study Procedures

5.1 Study Design

First, we will expand the treatment outline for COACH (see Appendix 1) into an initial treatment manual through meetings with content experts and stakeholder feedback. Next, we will develop fidelity checklists and revise the treatment manual through a "test run" with 2-3 couples. The resultant intervention will then be evaluated in an open trial with 12 veterans diagnosed with PTSD and their loved ones. During the course of the open trial, we will refine fidelity checklists and develop a provider training program. Using data obtained from the open trial, we will assess the intervention's acceptability, feasibility,⁴⁴ mechanisms, and outcomes. Lastly, using clinical observations, participant feedback from qualitative exit interviews, and additional stakeholder feedback, we will make final edits to the manual, yielding a manual suitable for a future RCT (Stage II Manual).²⁵ Upon completion of this proposal, we will be well positioned to apply for Merit funding for a randomized controlled efficacy trial.²⁵

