each. Treatment is typically between 13 and 15 sessions, but can be fewer or more based on patient need and symptom response. Consistent with IBCT, the treatment will take place in phases. The first phase focuses on gathering information from both the veteran and his/her loved one and creating a treatment frame that conceptualizes struggles in a fashion that is acceptable to both partners and that highlights ineffective change strategies. In COACH, this treatment frame also incorporates 1) the role of PTSD in disrupting relationships and intimacy, 2) the role of avoidance in maintaining PTSD and couple conflict, and 3) existing strengths or coping strategies that can be capitalized on in PE. In this way, the treatment frame serves as a contextualized and focused introduction to both key PE principles and key couples dynamics that will be challenged in treatment. In the 'active treatment' phase, sessions will focus on (1) reviewing *in vivo* exposure exercises completed at home, (2) shaping the couple's support for each other's efforts to practice a lifestyle of approach, and (3) imaginal exposure and emotional processing. The final session includes reflection on the therapy experience and building an action plan for continued work at home.

5.2B. Manual Expansion. In months 1-5, we will expand the treatment outline into an initial manual through weekly meetings with the investigator team ([name], [name], [name], [name], [name]). Our team is comprised of content experts in delivering and implementing PE ([name]; [name]' [name]) and couple therapy ([name], [name], [name]). The team will review, discuss, and revise intervention materials for each treatment session, led by [name]. This work will generate key questions for the first stakeholder meetings described below.

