5.2E. Manual Refinement. For any psychosocial intervention, critical insight is gained through actual delivery of the treatment. we will conduct a “test run” of the treatment manual with 2-3 cases. Early experience with these test cases will help identify sections of the treatment manual that prove difficult to implement or are unclear. The PI ([name]) and study Co-Investigator ([name]) will serve as the study providers. Of note, while [name] is a licensed psychologist, she is a Research Service employee and does not currently have Minneapolis VA privileges. She will treat cases under this IRB protocol and under the supervision of a privileged VA provider. After completing each of the sessions, Drs. [name] and [name] will compose a memo for the larger team that identifies (1) what went well and why, (2) what proved more challenging and why, and (3) time stamps from session recordings that correspond to these observations. Memoranda will be sent out to the team of investigators in advance and discussed in weekly intervention refinement meetings. The team will brainstorm solutions to problems and identify expansions needed to the manual to capture clinical observations. This work will generate the key questions for veteran and LO stakeholder meetings. These meetings will focus on problems with implementing ideas within the manual (e.g., “How can we help couples do a given at-home exercise more effectively?”). The study PI will draft manual revisions and distribute revisions to the team to review. During this time, [name] will also draft initial fidelity checklists, which will be reviewed and refined in team meetings.

5.3 Open Trial.

5.3A. Sample Identification & Recruitment. Participants will be ten veterans with PTSD at the Minneapolis VA and their loved ones. Although the Stage Model of Treatment Development does not recommend a sample size for stage 1B activities, published accounts of psychotherapy treatment development frequently report on samples of ten to twelve participants.⁴⁸⁻⁵¹ Veterans must meet full criteria for PTSD on the CAPS-5⁵² and have been in an intimate relationship for the last six months. Both members of the couple must be willing to participate together in therapy and deny any episodes of severe relationship violence in the past year. We will exclude veterans who are typically excluded from trauma-focused treatment due to counter-indications, including severe substance use, uncontrolled psychosis or mania, and

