Veterans will also complete a posttreatment structured clinical interview for PTSD symptoms.⁵² Veterans and LOs will also complete 90-minute semi-structured qualitative exit interviews. All interviews will be conducted in person or by phone, based on the interviewee's preference, and will be audio-recorded. Qualitative exit interviews (Appendix 2) will assess (1) attitudes about intervention components, structure (e.g., level of therapist contact), and materials (e.g., handouts), (2) acceptability and efficacy of COACH, including suggestions for intervention improvement, (3) engagement with COACH, including retention and barriers/facilitators to engaging with the program, (4) perceptions of the impact of the program on the intervention targets (e.g., functioning, social control, subjective norms, and LO reliance) and exploration of unexpected domains impacted by the program, and (5) the completeness and time burden of the survey battery. We will also extract the following administrative data: (1) the number of sessions attended (from electronic medical record; retention), (2) the number of participants screened each month (screening), and (3) the number of eligible Veterans and LOs who declined participation (recruitment), and therapists ratings of homework compliance using two

5.6A. Risk to Subjects

A.1. Human Subjects Involvement and Characteristics

We aim to enroll 12 Veterans with PTSD at the Minneapolis VA and their loved ones. Veterans must (1) meet full criteria for PTSD on the CAPS⁵² and (2) have been in an intimate relationship for the last six months. Both members of the couple must be (3) willing to participate together in therapy, and (4) deny any episodes of

items adapted from the Patient Exposure and Response Prevention Adherence Scale (PEAS) for Obsessive Compulsive Disorder (also a cognitive-behavioral exposure therapy).⁶²

Table A. Data Sources					
Reporter	Baseline	During Treatment	Posttreatment	3-month follow-up	
Veteran	Structured Interview	Surveys assessing symptoms, weekly questions in preparation for therapy sessions for therapists, and treatment mechanisms	Structured Interview	Online measures	
	Online survey measures		Online survey measures		
			Qualitative Interview		
LO	Online survey measures	Surveys assessing symptoms, weekly questions in preparation for therapy sessions for therapists, and treatment mechanisms	Online survey measures Qualitative Interview	Online measures	

A.3. Potential Risks

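### The one-session-per-couple fidelity draw in 6.2 is not stratified by phase, so under plausible assumptions there is about a 41% chance that no final session is ever rated

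*Combined protocol and SAP*

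**What the plan says.** Section 6.2 states that every therapy session is recorded and then: "We will apply the fidelity checklists to one randomly selected session for each couple". The purpose follows directly: "We will identify gaps in content covered by checklist items and items that are unclear, difficult to rate, or not consistently applicable". Items are then revised and finalised for the Stage II manual. Treatment fidelity is also a feasibility outcome under Aim 2 and in Table 1, and section 7.2 plans descriptive statistics and graphs for it.

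Section 5.2A gives the structure of treatment: "Consistent with IBCT, the treatment will take place in phases". It describes an opening phase of information gathering and treatment framing, an active phase whose sessions have three components in common, and a final session given to reflection and an action plan. On length it says: "Treatment is typically between 13 and 15 sessions, but can be fewer or more based on patient need and symptom response". It does not say how many sessions the framing phase takes.

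The number of couples differs between sections. Section 5.1 has "The resultant intervention will then be evaluated in an open trial with 12 veterans diagnosed with PTSD and their loved ones", and section 5.6A agrees on 12. Section 5.3A has "Participants will be ten veterans with PTSD at the Minneapolis VA and their loved ones" and plans one couple per month over 10 months.

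The plan does not mention stratifying the draw by phase, a minimum number of ratings per phase, or what to do when a couple stops early.

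**The concern.** The ratings have two jobs. They summarise fidelity, and they test the checklist before it goes into the manual for a randomised trial. The second job needs coverage: a checklist section that is never applied to a recording cannot show that its items are unclear, hard to rate or inapplicable. An unstratified draw rates each phase roughly in proportion to its number of sessions. The active phase will be rated many times. The final session, which occurs at most once per couple, may not be rated at all, and the framing phase may be rated only once. At stake is whether the closing-session items, and to a lesser extent the framing items, have been tried on a real session in this step before they are finalised.

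**Working it through.** The plan gives no coverage figure to reproduce. The check treats the draw as independent across couples and uniform over a couple's sessions; 6.2 says only that selection is random.

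**Inputs**
- Couples: n = 12 (sections 5.1 and 5.6A), or 10 (section 5.3A).
- Sessions per couple: k = 14, the midpoint of the typical 13 to 15 in section 5.2A (assumption), with 13 and 15 as the range.
- Framing phase: f = 3 sessions (assumption; length not stated), with 2 and 4 as the range.
- Final session: 1 per completed course.

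**Final session never rated.** P = (1 − 1/k)^n.

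| Sessions (k) | 12 couples | 10 couples |
|---|---|---|
| 13 | (12/13)^12 = 38.3% | (12/13)^10 = 44.9% |
| 14 | (13/14)^12 = 41.1% | (13/14)^10 = 47.7% |
| 15 | (14/15)^12 = 43.7% | (14/15)^10 = 50.2% |

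**Early stopping.** If a share d of couples never reaches the final session, and completers keep a 1/14 chance of having it drawn, P = (d + (1 − d) × 13/14)^12. The plan gives no expected dropout for this trial, so d is an assumption. The upper end, 60%, is the non-completion rate of the veteran sample cited in section 2.0.
- d = 20%: 0.9429^12 = 49%
- d = 40%: 0.9571^12 = 59%
- d = 60%: 0.9714^12 = 71%

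**Framing phase** (12 couples, 14 sessions). The number of framing ratings is Binomial(12, f/14). P(none) = ((14 − f)/14)^12. P(exactly one) = 12 × (f/14) × ((14 − f)/14)^11.
- f = 3: none 5.5%, exactly one 18.1%, so at most one 24%
- f = 2: none 15.7%, exactly one 31.5%, so at most one 47%
- f = 4: none 1.8%, exactly one 8.5%, so at most one 10%

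**Active phase.** With f = 3 there are 14 − 3 − 1 = 10 active sessions. P(none rated) = (4/14)^12, or about 3 in 10 million.

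**Would balancing over session numbers be enough?** Drawing 12 of 14 numbers without replacement leaves 14 − 12 = 2 unrated, and a given number is missed with probability 2/14 = 14.3%. With 10 couples, 4 are unrated and the probability is 4/14 = 28.6%. Because length is flexible, a fixed number such as 14 is also not the closing session of a couple who finish at 13 or 15. The final session has to be assigned as a phase.

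**The case against.** The strongest reply is that missed session numbers are not missed content. A reader could compute that 14 × (13/14)^12 = 5.75 of 14 session numbers are expected to go unrated and infer that about six kinds of session go untested. The documents do not support that. Section 5.2A describes phases, not 14 kinds of session, and the active sessions share their components. The objection stands on this point and confines the problem to the final session and to thin coverage of framing.

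Second, other activities examine content. Section 5.2E has the checklists drafted during the test run with 2 to 3 couples and refined in team meetings, with a provider memo after each session. Section 6.3 has the two providers meeting weekly and reviewing portions of recordings. So the content would not go unexamined. But none of this is described as applying the checklist to a recording, so it does not replace a rating.

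Third, a uniform draw per couple estimates the fidelity of an average session without weights, whereas phase quotas change that target. This is correct, and the remedy must include reporting by phase or weighting.

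Fourth, 6.2 does not say the draw is unstratified. Also correct: what can be said is that no stratification is stated.

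Finally, this is a small open trial with descriptive fidelity reporting, no threshold, and an instrument still being developed. No inference or participant protection depends on the draw. That limits the severity.

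**Conclusion.** The concern holds in a limited form. As written, the draw has about a two-in-five chance of rating no final session: 41% with 12 couples and 14 sessions, 38% to 44% for 13 to 15 sessions, 48% with ten couples and 14 sessions, and 49% to 71% if 20% to 60% of couples stop before the end. The chance of at most one framing rating is 24% if that phase lasts 3 sessions. These figures rest on independent, equally likely draws, an assumed session count and, for framing, an assumed phase length.

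Two stronger inferences should be resisted. The fidelity summary would not be silent on whole phases in general: total omission of a 3-session framing phase has a 5.5% chance, and omission of the active phase is practically impossible. Nor would spreading the draw over session numbers settle the matter, since 12 ratings still miss 2 of 14 numbers and flexible length means a number does not identify the closing session. Stratifying by phase is the better method, at the same number of ratings. Minor severity.

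**What to change.** In section 6.2, keep one rated session per couple and add the following:

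- Stratify the random draw by phase (framing, active, final), with the final session rated for at least one or two couples who complete treatment.
- If a couple did not reach its assigned phase, rate a random attended session from that couple and reassign the unfilled phase to a later couple. Placing the final-session assignments early in the list leaves room for this.
- Report fidelity by phase. For a whole-course summary, weight by the number of sessions per phase (for example 3/14, 10/14 and 1/14 under the assumptions above).

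Separately, reconcile the ten couples of section 5.3A with the 12 of sections 5.1 and 5.6A, since this sets the number of ratings to allocate.

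The cost is an allocation list and phase-wise or weighted reporting. No extra ratings or recordings are needed, because every session is already recorded. The closing-session items are then tested on a recording as long as at least one couple assigned to that phase completes treatment.

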Our overall goal is to develop and pilot a couple-therapy approach to Prolonged Exposure that integrates loved ones into every session of PE. We will combine techniques from Integrative Behavioral Couples Therapy and a brief, three-session approach to involving family in PE (Partner Enhanced Prolonged Exposure). We anticipate this intervention will teach couples to embrace a lifestyle that supports confronting trauma-related distress, so the veteran can achieve optimal functional recovery, while improving both social and family functioning. We will complete stages 1A and 1B of the Stage Model of Treatment Development.²⁵ This includes the following aims:

Aim 1: Expand our treatment outline using content experts and feedback from key **stakeholders** (veterans, loved ones, providers, and VA mental health leadership).

Aim 2: Conduct a pilot **open trial** to assess (a) the acceptability of treatment components, structure, and materials, (b) the feasibility of the intervention (retention and intervention fidelity), and (c) the study approach (screening, recruitment, and assessment process).

Aim 3: Explore the preliminary effects of the intervention on select outcomes including overall functioning, mental health functioning, social functioning, family functioning, and potential mechanisms (social control, subjective norms, and the degree to which veterans rely on their partners for support).

Impact: PTSD treatments (including PE and CPT) have been criticized for a narrow focus on symptom gains over goals that may be more meaningful to veterans, such as greater quality of life, interpersonal connections, and social functioning.^{26,27} Our proposal aims to expand the explicit targets of PE to these patient-centered outcomes. If our approach to a couple-based exposure therapy demonstrates promise, this proposal could provide the first step in a series of studies that **feed the evolution of one-on-one symptom-focused psychotherapies into family-based interventions designed to lift the whole household**. Our approaches could inform adaptations to interventions for a myriad of problems including suicide prevention, TBI rehabilitation, and pain management, contributing to a broader evolution towards evidence-based, family-inclusive care focused on outcomes with meaning to veterans.

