fidelity, screening, and treatment retention will be generated. We will calculate rates of survey non-response and item missingness for assessment feasibility. To preliminarily evaluate outcomes, we will calculate and graphically display the direction and magnitude of change from baseline to follow-up for outcomes outlined in Table 1. We will also calculate the percentage of participants who improved, worsened, and experienced no change for each of these measures. We will calculate descriptive statistics and pre-to-post treatment effect sizes. Lastly, we will triangulate our quantitative data with qualitative themes through matrices with exemplary quotations. Themes that emerge from the interviews will be stratified by participants' scores on relevant quantitative scales (e.g., participants' acceptability themes stratified by their Credibility-Expectancy and Satisfaction scores; feasibility themes stratified by number of sessions attended).

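### The Aim 2(b) fidelity result rests on ratings that are also used to revise the checklist, and no planned rating is assured to use the final version

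*Combined protocol and SAP*

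**What the plan says.** Section 3.0 defines intervention feasibility in Aim 2(b) as retention together with fidelity. Table 1 in section 6.1 gives fidelity its own row and footnotes the instrument as one created within the study. Section 7.2 promises descriptive statistics and graphs in which intervention "fidelity, screening, and treatment retention will be generated". It sets no fidelity threshold and names no checklist version.

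The checklist has a history before the open trial. In section 5.2E, during the test run with 2-3 couples, a team member "will also draft initial fidelity checklists, which will be reviewed and refined in team meetings". Section 5.1 then says: "During the course of the open trial, we will refine fidelity checklists and develop a provider training program".

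The ratings are described in section 6.2. Every session is recorded. "We will apply the fidelity checklists to one randomly selected session for each couple". The next sentence gives a development use for that exercise: "We will identify gaps in content covered by checklist items and items that are unclear, difficult to rate, or not consistently applicable". Then: "Items will be revised and finalized for the final Stage II Manual".

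On the manual, section 6.3 says of the weekly and monthly meetings held during the open trial: "These discussions will be used to refine and expand the manual and to identify key questions for stakeholder meetings". Section 5.1, by contrast, says that the intervention emerging from the test run is the one the open trial evaluates, with final manual edits coming last.

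**The concern.** One small set of ratings has two jobs. It shows which checklist items do not work, and it supplies the fidelity figure for Aim 2(b). Nothing in 6.2 or 7.2 separates the two uses, freezes a version, or calls for a rating with the finished instrument.

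If the reported figure comes from the development ratings, a low score can mean poor delivery, or it can mean an item the team itself judged unclear or inapplicable. The data as planned cannot separate these. The stated next step is a randomized trial using the Stage II manual and its checklist. That trial would inherit a fidelity figure not assured to come from the checklist it adopts. There is little other fidelity evidence to fall back on, because only one session per couple is rated.

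**Working it through.** The plan states no fidelity figure, so there is nothing to reproduce. The check is a reading of the sequence, with simple counts.

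**Inputs.** Couples: 12 (section 5.1) or 10 (section 5.3A). Rated sessions per couple: 1 (6.2). Sessions per couple: typically 13 to 15, of 90 minutes each (5.2A). Number of checklist versions used for scoring: not given.

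**How much is rated.**
- Ratings = couples × 1 = 12 (or 10).
- All sessions = 12 × 13 to 12 × 15 = 156 to 180 (10 couples: 130 to 150).
- Share rated = 1/15 to 1/13 = 6.7% to 7.7%.

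**Which version is used.** Three readings of 5.1 and 6.2 can be set side by side.

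| Reading | Ratings comparable across couples? | Ratings on the final checklist |
|---|---|---|
| One version used for every couple, revised afterwards | Yes, all 12 (10) | None, unless no item needs changing |
| Items revised as the trial proceeds | Only within a version | Only those made after the last revision; number unknown |
| Checklist finished first, recordings then scored | Yes, all 12 (10) | All, but this needs a scoring round the text does not describe |

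The third reading is not excluded, since recordings can be rated late. But 6.2 presents applying the checklist as the way faults are found, so those ratings come before the final items. A further round with the final items would have to be added, and none is stated. Under the two readings the text does describe, no rating is assured to be on the final version.

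**What a version split would do (illustration only).** Assume equal-sized versions: two give 12/2 = 6 ratings each (10/2 = 5), and three give 12/3 = 4 each (10/3, about 3). Assume also that each rated session is classed as meeting or not meeting some criterion (the plan has none) and that all meet it. The exact 95% lower limit is then 0.025^(1/n):
- n = 12: 73.5%
- n = 6: 54.1%
- n = 4: 39.8%

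Reporting by version would therefore leave little information in each part, so one frozen version for all couples is better than stratifying afterwards.

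**The manual.** Section 6.3 feeds discussions during the trial into manual refinement. Section 5.1 describes the evaluated intervention as the product of the test run. In Table 2 (section 5.5) the manual-refinement row carries the same marks as the test-case row. These do not settle whether an edit made during the trial changes what a later couple receives, and no manual version is logged per rated session.

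**The case against.** A reader might infer that the fidelity result pools scores from different instruments. The documents do not establish that. The order of sentences in 6.2 fits a single version applied to every selected session and revised afterwards. Nowhere is it said that revised items are used on later couples or that scores from different versions are combined. Sections 5.1 and 6.2 make revision during the trial plausible, no more, and any split of the ratings by version is assumed.

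A reader might also infer that the manual changes under the couples throughout the trial, or that the final checklist will have no fidelity data at all. Neither follows. Section 6.3 does not say when edits take effect, and 5.1 and Table 2 point the other way. Only problem items are described as prompting revision, so unchanged items keep their data.

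The rest of the defence is fair. The open trial does not begin with an untried checklist, because 5.2E has it drafted and refined in the test run. Refining it is a declared purpose of a Stage 1A/1B study. The analysis is descriptive, with no threshold, test or go/no-go rule for fidelity. It can also be said that re-scoring recordings with items tuned on those same recordings is still in-sample. That last point stands and shapes the fix.

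None of this supplies the missing step. Even on the most favourable reading that 6.2 describes, with one version throughout, the reported scores come from a superseded checklist as soon as any item is changed.

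**Conclusion.** The point holds in limited form. The Aim 2(b) fidelity figure is to come from 10 or 12 ratings that are also used to revise the checklist, and none of them is assured to use the finished version. That conclusion needs no assumption about how many versions there are; it rests on the absence of any stated scoring step after finalization. Comparability across couples is a further, conditional problem that arises only if items are revised during the trial and used for scoring. The timing of manual edits is unclear rather than shown to be harmful.

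No inferential result changes. What is affected is how the fidelity figure can be interpreted and carried into the next trial. The change is worth making because it alters the source of a named outcome at low cost, but the study does not fail without it.

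**What to change.** In section 6.2, state that ratings made while the checklist is under development serve only to revise it. Once it is frozen, score one randomly selected recording per couple with it. Preferably this is a second random recording that played no part in revising items. Where that is not possible, for example when a couple has only one recorded session, use the same recording and state the in-sample limitation.

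In section 7.2, base the fidelity statistics on those scores alone. Record the manual version in force at each rated session. Report each score as the percentage of applicable items, with the number of applicable items beside it, so that differing denominators across couples are visible.

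Cost: 10 × 1.5 h = 15 h to 12 × 1.5 h = 18 h of listening for one existing rater, plus a version field. A second rater or extra scoring time would add to this. No new sessions or staff are needed, since every session is already recorded. The fidelity result will be available later, after the checklist is final. Checklist development itself is unchanged.
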